### **8.3. Concomitant and Other Medications**

Concomitant medications are coded using the World Health Organization drug dictionary (B3 Global September 2018) for anatomical therapeutic chemical (ATC) classification and preferred drug name. Patients who used multiple medications are counted only once for each ATC and preferred drug name. Anatomical therapeutic chemical (ATC) and preferred drug name within each ATC are sorted alphabetically. Coded concomitant medications are summarized by treatment analysis group (Section 4.5). Percentages are based on the number of patients in the safety analysis set.

A concomitant medication is any medication taken at the time of first study treatment during the 402-C-1803 study or a medication that was started after the start of 402-C-1803 study drug dosing.

Specifically, concomitant medications are medications:

- That are continued from 402-C-1603 or 402-C-1808 and continued after the first study drug dosing, or
- That have start dates within the 402-C-1803 treatment period.

Concomitant medications are summarized for each treatment analysis group by World Health Organization ATC class and preferred name. Patients may have more than 1 medication per ATC class and preferred name. At each level of patient summarization, a patient is counted once if he/she reported one or more medications at that level. Each summary is ordered by descending order of incidence of ATC class and preferred name within each ATC class.

Concomitant medications include those with an end date after the first study drug administration as well as medications without an end date. Medications with an end date on or prior to the date of first study drug administration in 402-C-1803 study are not considered concomitant medications.

Patients who take the following excluded medications (defined in the Protocol Section 9.3.1) during the study are listed.

- Any other investigational drug
- Tolvaptan (patients on tolvaptan who have already enrolled under Version 3.0 of the protocol may remain in the trial)
- Somatostatin analogues
- Chronic (> 2 weeks) immunosuppressive therapy, or need for corticosteroids, including therapies such as glucocorticoids, oncologic preparations, and anti-tumor necrosis factor  $\alpha$  agents [eg, infliximab (Remicade®), adalimumab (Humira®), certolizumab pegol (Cimzia®), etanercept (Enbrel®)]. (Glucocorticoid intra-articular injections, inhaled products, topical preparations, and nasal preparations are allowed.)

In addition, patients who take the following concomitant medications (defined in the Protocol Section 9.3.2) during the study are listed.

- Antibiotics;
- Daily multivitamins or recommended daily supplements;
- Other medications intended to manage concurrent diseases, as authorized by the treating physician;
- Statins, in the Czech Republic and globally
- Pain management medications
- Oral, implantable, or injectable contraceptives

### **8.3.1. Missing and Partial Concomitant and Other Medication Start and Stop Dates**

Missing and partial concomitant medication start and stop dates are detailed in Section 6.6.2

## **8.4. Clinical Laboratory Evaluations**

Laboratory data are summarized at baseline and at each time point by treatment analysis group (Section 4.5).

### **8.4.1. Continuous Summaries of Laboratory Results**

Selected laboratory evaluations and change from baseline are summarized by treatment analysis group (Section 4.5), laboratory category (hematology, chemistry), test, and study visit using continuous statistics. The eGFR results are calculated using formulas described in Section 6.5.6.

Box plots and line graphs are generated for selected laboratory test results, such as eGFR, ACR, alanine aminotransferase (ALT), aspartate aminotransferase (AST), total bilirubin (TBL), B-type natriuretic peptide (BNP), blood urea nitrogen, uric acid, magnesium, creatinine, and creatine kinase. Line graphs include mean  $\pm$  SE over time for both the observed values and for change from baseline.

Due to the nature of urinalysis parameters, summaries of continuous statistics are not provided unless otherwise specified. The one exception is the ACR from the FMV urine collection. Qualitative lab results, including urinalysis, are included in the listings, but are not summarized.

Laboratory results that are above or below normal limits are flagged in the listings.

#### **8.4.1.1. Urine Albumin/Creatinine Ratio**

Summaries of ACR (Section 6.5.7) will use the geometric mean with 95% confidence intervals instead of the arithmetic mean and will display ACR results in original units of mg/g. Changes from baseline in ACR are reported as the post-baseline/baseline ratios and are summarized by geometric means with 95% confidence intervals at each time point. Summaries of ACR will use the geometric mean instead of the arithmetic mean. Presentations will display ACR results in the original units (mg/g). Changes in ACR are calculated as the ratio of each visit to baseline.

Additionally, ACR is summarized by baseline ACR quartile. Descriptive summaries at each visit include the geometric mean of ACR, SD as well as the geometric mean of percent change from baseline. Summaries of ACR exclude values within the Week 2 and Week 6 visit windows.

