7.8. Schedule of Assessments

[Table 5](#) lists the overall schedule of assessments for the study.

Table 5: Schedule of Assessments

Assessment	Study Week (Day±Days)	Screening Visit ^a	Day 1 ^{a,c}	Week 1 (Phone) Day 3 ± 2 Days	Week 1 Day 7 ± 3 Days	Week 2 (Phone) Day 10 ± 2 Days	Week 2 Day 14 ± 3 Days	Week 3 (Phone) Day 21 ± 2 Days	Week 4 Day 28 ± 3 Days	Week 4 (Phone) Day 31 ± 2 Days	Week 5 (Phone) Day 38 ± 2 Days	Week 6 Day 42 ± 3 Days	Week 7 (Phone) Day 45 ± 2 Days	Week 8 Day 56 ± 3 Days	Week 12 Day 84 ± 3 Days	Week 24 ± 3 Days, Every 24 Weeks ± 3 Days	End of Study Visit ^b
Informed consent		X ^c	X ^c														
Inclusion/Exclusion		X	X														
Demographics ^d		X	X														
Prior and Concomitant medications		X	X	X	X	X	X	X	X	X	X	X	X	X	X	X	X
Medical History		X	X														
Height		X	X		X		X		X			X		X	X	X	X
Weight at home			X	X	X	X	X	X	X	X	X	X	X	X	X	X	
Weight in-clinic		X	X		X		X		X			X		X	X	X	X
Dispense Weight & Study Drug Diary			X				X		X			X		X	X	X	
Collect/Review Weight & Study Drug Diary				X	X	X	X	X	X	X	X	X	X	X	X	X	X
Vital sign measurements		X	X		X		X		X			X		X	X	X	X
Physical examination		X	X		X		X		X			X		X	X	X ^e	X ^e
Pregnancy test ^f			X													X	
Dispense study drug			X				X		X			X		X	X	X	
Collect study drug							X		X			X		X	X	X	X
Telephone contact				X		X		X		X	X		X				
Adverse event collection			X	X	X	X	X	X	X	X	X	X	X	X	X	X	X
Basic Lipid Panel			X													X	X
Clinical Chemistries (incl. eGFR) ^g		X	X		X		X		X			X		X	X	X	X
BNP and NT-Pro BNP		X	X		X		X		X			X		X	X	X	X
Hematology		X	X		X		X		X			X		X	X	X	X
Urine collection for ACR ^h		X	X						X					X	X	X	X
Tanner Staging ⁱ			X													X	X

Abbreviations: AE=adverse event; BNP=B-type natriuretic peptide; eGFR=estimated glomerular filtration rate; NT-proBNP=N-terminal prohormone B-type natriuretic peptide; ACR=albumin to creatinine ratio; WOCBP=women of child-bearing potential

^a A screening visit will be conducted for subjects whose planned EAGLE Day 1 visit is not within 8 weeks of the eligibility lab assessments from the prior qualifying study. Refer to Section 7.1 for additional details. Subjects requiring a screening visit will be consented prior to the start of any screening assessments. All other subjects will be consented at the start of the Day 1 visit, before any procedures are performed for this, or the prior study.

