9.9.17. Urine Collection for Albumin to Creatinine Ratio (ACR)

Albumin/creatinine ratio will be measured by first morning void spot urine collection as indicated in [Table 5](#). Appropriate containers for the collection will be provided to the patient at the visit prior to the collection.

Patients should be instructed how to properly capture a sample of their first morning void, defined as their first urination on the day of collection. Following Day 1, if a patient presents for a visit and has forgotten to collect (or bring) the urine sample(s) for that visit, they may return within 7 days to submit the sample(s) collected that day.

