#### 6.5.4. Visit Windows

**Table 2: Visit Window (Days)**

Analysis Visit	Label	Target Study Day	Analysis Window
0	Day 1	1	1
1	Week 1	7	$2 \leq \text{Study Day} \leq 10$
2	Week 2	14	$11 \leq \text{Study Day} \leq 21$
4	Week 4	28	$22 \leq \text{Study Day} \leq 35$
6	Week 6	42	$36 \leq \text{Study Day} \leq 49$
8	Week 8	56	$50 \leq \text{Study Day} \leq 70$
12	Week 12	84	$71 \leq \text{Study Day} \leq 126$
24	Week 24	168	$127 \leq \text{Study Day} \leq 210$
48	Week 48	336	$308 \leq \text{Study Day} \leq 364$
72	Week 72	504	$476 \leq \text{Study Day} \leq 532$
96	Week 96	672	$644 \leq \text{Study Day} \leq 700$
120, 144, etc.	Week 120, Week 144, Every 24 Weeks Thereafter	Analysis Visit $\times$ 7	$([\text{Analysis Visit} \times 7] - 28) \leq \text{Study Day} \leq ([\text{Analysis Visit} \times 7] + 28)$
FU	Follow-up	28 days after last dose	$14 \leq \text{Days after last dose}^a \leq 35$

a For safety analyses, last dose for patients completing the treatment or permanently discontinuing study drug that occur on the date of last dose or less than 14 days after last dose are considered on treatment.

The safety follow-up is based on days since last dose. If more than one assessment exists during the follow-up after last dose, the one closest to 28 days following the date of the last study drug administration is used for analysis and summary.

If a parameter is assessed or measured more than once within a visit window, the one that is closest to the protocol-scheduled time point (or target study day) is used for the purposes of data analysis and summary. If two assessments are equidistant from a target study day, the earlier assessment is used. If the visit used for analysis includes two assessments on the same day, the average of assessments will be used for non-laboratory parameters. For laboratory parameters, if both an original and retest result are available in the laboratory dataset, the original result will be used and the second (ie, “retested”) result will be ignored. Records from visits not closest to the target study day, and therefore not used in analyses, are presented in by-subject data listings.

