## 10. COVID-19 IMPACT

### 10.1. Operational Impact

The COVID-19 pandemic has impacted the conduct of the study per protocol. The mitigation strategies are adopted to protect the health of participants in the 402-C-1803 study, while maintaining compliance with good clinical practice and minimizing the risk to trial integrity (Protocol Appendix 1). These measures apply to United States and rest of the world. An eCRF form is updated to collect data for COVID-19 impact.

The number and percentage of patients impacted by COVID-19 are summarized by visit and treatment analysis group for the following categories:

- Visit impact
  - Visit not done
  - Visit conducted out of window
  - One or more procedures could not be performed
  - Rollover delayed
- Data collection methods
  - No change (occurred as expected per protocol)
  - Telephone visit
  - Video conference visit
  - Home health care visit
  - Local lab
  - Other
- Drug dispensation methods
  - No change (office visit)
  - Investigational product dispense not scheduled (telephone visit)
  - Mailed to patient
  - Home health care provided
  - Dose not escalated
  - Dose de-escalated
  - Other

The number and percentage of patients impacted by COVID-19 are summarized by treatment analysis group (Section 4.5) for the following categories:

- Drug Interruption due to COVID-19
  - Tested positive for COVID-19 (yes, no, not tested)

- Primary reason for interruption (medical monitor/sponsor recommendation, site mandate, patient choice, insufficient investigational product supply, other)

Patient narratives are provided for all patients who test positive for SARS-CoV-2, the causative agent of COVID-19.

Early discontinuations of treatment or study due to COVID-19 are summarized and listed (specified in Section 7.1).

All deviations due to the impacts of COVID-19 are identified and documented accordingly by the site and the sponsor. The failure to complete a protocol visit is not considered as a reason for study discontinuation and/or a major deviation. All COVID-19–related deviations will be identified in the protocol deviation listing (Section 7.3).

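### The SAP's exclusion of the Week 6 window drops some protocol-compliant Week 4 ACR samples (Days 36-38) from the by-visit ACR summaries

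*SAP*

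**What the plan says.** The schedule in Protocol 7.8 (repeated as SAP Table 1) marks the row "Urine collection for ACR" at screening, Day 1, Weeks 4, 8, 12 and 24, every 24 weeks, and the End of Study visit. Weeks 1, 2 and 6 carry no ACR.

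The Week 4 column is headed "Week 4 Day 28 ± 3 Days". Under Protocol 9.9.17, a patient who comes to a visit after Day 1 without the urine sample has a grace period: "they may return within 7 days to submit the sample(s) collected that day". The sample is collected on the day it is handed in, so that later date is its collection date.

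SAP 6.5.4, Table 2, has one set of windows for all parameters. Week 4 covers study Days 22-35, Week 6 covers Days 36-49 and Week 8 covers Days 50-70. When a window holds several values, "the one that is closest to the protocol-scheduled time point (or target study day) is used for the purposes of data analysis and summary". SAP 8.4.1.1 then states: "Summaries of ACR exclude values within the Week 2 and Week 6 visit windows". The SAP gives no ACR-specific window and no rule that returns a late sample to the visit it was meant for.

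**The concern.** The windows were built for laboratory tests drawn at every in-person visit, and ACR is not drawn at Week 6. A sample that is late but still within protocol for Week 4 can therefore cross into a window that has no scheduled ACR. The exclusion sentence then removes it instead of returning it to Week 4. The same happens to a Week 4 visit held late, or a Week 8 visit held early, if the sample falls on Days 36-49. The SAP expects some irregular timing: its COVID-19 section tabulates "Visit conducted out of window".

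Change from baseline in ACR is named among the primary safety endpoints (Protocol 6.2, SAP 3.2.1). Missing values are not imputed (SAP 6.6.1), so nothing fills the gap in the Week 4 row.

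**Working it through.** The plan states no figure to reproduce. The check is day arithmetic.

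**Inputs**
- Week 4 visit: Day 28 ± 3, so Days 25-31 (Protocol 7.8).
- Late return: up to 7 days after the visit (Protocol 9.9.17).
- Windows: Week 4 = 22-35, Week 6 = 36-49, Week 8 = 50-70, Week 12 = 71-126, Week 24 = 127-210, later visits target ± 28 (SAP Table 2).

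**Latest compliant Week 4 sample**
- 31 + 7 = Day 38. The Week 4 window ends at Day 35, so Days 36, 37 and 38 are compliant with the protocol but labelled Week 6.

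**Which combinations are affected**
- The sample is lost when visit day + delay ≥ 36.
- Visit Day 29: delay of 7 days (1 combination).
- Visit Day 30: delay of 6 or 7 days (2 combinations).
- Visit Day 31: delay of 5, 6 or 7 days (3 combinations).
- A visit on Day 28 with the full delay gives 28 + 7 = Day 35, which is kept, as is any earlier visit.
- Total 1 + 2 + 3 = 6. There are 7 visit days × 7 delays = 49 late-return combinations, so 6/49 = 12.2%. Counting same-day samples as well, it is 6 of 7 × 8 = 56.

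**Sensitivity to day numbering**
- If the protocol's Day 28 means 28 days after Day 1 (SAP study day 29), the latest sample is Day 39, and 10 of 49 late-return combinations (10 of 56 overall) are lost.

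**Other ACR visits: latest compliant late return against window end**

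| Visit | Latest sample | Window end | Lost? |
|---|---|---|---|
| Week 4 | 31 + 7 = 38 | 35 | Yes, Days 36-38 |
| Week 8 | 59 + 7 = 66 | 70 | No |
| Week 12 | 87 + 7 = 94 | 126 | No |
| Week 24 | 171 + 7 = 178 | 210 | No |
| Week 48 onward | target + 10 | target + 28 | No |

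**Out-of-window visits**
- A delayed Week 4 visit sampled on Days 32-35 stays in Week 4. It is lost from Day 36, which is 36 - 31 = 5 days past its protocol window.
- A Week 8 visit is lost if sampled on Day 49 or earlier, which is at least 53 - 49 = 4 days before its protocol window opens.

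**Nearest scheduled ACR visit**
- The midpoint of the two targets is (28 + 56)/2 = Day 42. Days 36-41 lie nearer Week 4 and Days 43-49 nearer Week 8. Day 42 is a tie.

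**The case against.** The rule has a sensible purpose. No ACR is scheduled at Week 2 or Week 6, so the exclusion avoids sparse, self-selected rows in the by-visit table. The study is descriptive and untested, and an affected patient who stays in the study still has ACR due at Week 8 and later. All of this stands, but it supports suppressing a Week 6 row, not discarding a valid Week 4 sample.

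Four stronger readings are tempting, and the documents do not support them.
- A reader might infer that a high value on Days 36-49 is also left out of the shift table and the count of patients above 3500 mg/g. The exclusion sentence sits in 8.4.1.1, among the continuous by-visit summaries. SAP 8.4.2 defines the worst on-treatment value and the any-time threshold without visit windows. The broad wording of the exclusion leaves its scope open to question, which is a reason to clarify it and not evidence of loss.
- A reader might infer that the values disappear altogether. SAP 6, 6.5.4 and 8 send unused values to the listings.
- A reader might take 12% as a share of patients. It counts calendar combinations among late returns, with every visit day and delay equally weighted.
- A reader might infer that the gap hides the time when an ACR rise first appears. Protocol 5.1.2.6 describes increases in urinary albumin but gives no time of onset.

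The dose objection to widening the Week 4 window is also fair. The earliest compliant Week 6 visit is 42 - 3 = Day 39, so a sample relabelled Week 4 from Days 39-42 may follow the Week 6 dose step. Compliant late returns on Days 36-38 precede that visit.

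**Conclusion.** The point holds for the by-visit ACR summaries. As written, the SAP removes protocol-compliant Week 4 ACR samples dated Days 36-38, together with out-of-window Week 4 or Week 8 samples dated Days 36-49. Week 12 and later are unaffected, and so are Week 8 samples collected within protocol.

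The size is probably small. Compliant loss needs both a Week 4 visit on Days 29-31 and a return 5-7 days later. The documents do not give the late-return rate. If 5% to 20% of patients returned the Week 4 sample late (an assumption), with visit days and delays spread evenly (a further assumption), then 0.05 × 6/49 = 0.6% to 0.20 × 6/49 = 2.4% of Week 4 samples would be lost. The number of out-of-window visits is also unknown.

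The result assumes that the protocol's Day 28 is SAP study day 28; a one-day shift makes the loss slightly larger. Priority is minor: the correction is worth making because it is cheap and concerns a named primary safety endpoint.

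**What to change.** In SAP 6.5.4 and 8.4.1.1, replace the exclusion sentence with an ACR-specific rule:
- Assign a late-returned sample to the nominal visit it belongs to. At minimum, extend the ACR Week 4 window to Day 38.
- Assign other ACR samples on Days 36-49 to the nearest scheduled ACR visit: Days 36-42 to Week 4 and Days 43-49 to Week 8. The Day 42 tie must be stated, because the SAP's tie rule covers two assessments around one target and not one assessment between two targets.
- Keep the existing closest-to-target selection within each window.
- State that the by-visit rule does not restrict the worst on-treatment shift table or the any-time count of ACR above 3500 mg/g in 8.4.2, which use all ACR values that those definitions cover.

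Under the first step, all 56 permitted Week 4 combinations are kept, against 50 now. The cost is a few lines of SAP text and one parameter-specific window in programming. The downside is that a Week 4-labelled sample from Days 39-42 may follow the Week 6 dose step; a table footnote can say so. If that mixing is unwelcome, the Day 38 limit alone covers the compliant samples.

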#### **8.4.1.2. Continuous eGFR**

Any eGFR values collected after starting dialysis or after receiving a kidney transplant are treated as missing. Missing values are not imputed as specified in Section 6.6.1.

The change from baseline in eGFR is summarized by visit and treatment analysis group (Section 4.5). Summary statistics and change from baseline are presented by visit window (Section 6.5.4). Waterfall plots of eGFR change from baseline, labeled by treatment analysis group (Section 4.5) are generated at each visit window. Results are presented in tables and plots.

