8.5. Discontinuation

Discontinuation refers to a patient's permanent stopping of administration of study drug and all study assessments and visits for a patient, site, or study. Patients have the right to discontinue study drug and withdraw from the study at any time for any reason, without prejudice to their medical care. Furthermore, the investigator may discontinue a patient from study drug and the sponsor may terminate a specific site or the entire study. Consultation with the medical monitor should occur prior to study drug discontinuation and withdrawing a patient from the study. The reason for a patient's discontinuation from study drug or study termination will be recorded in the electronic case report form (eCRF).

Patients who permanently discontinue from study drug will be asked to complete the End-of-Study procedures noted in [Table 5](#), and withdraw from the trial.

If a patient reaches ESKD (defined as the initiation of maintenance dialysis for 12 weeks or more or kidney transplant), the patient must terminate from the study and should complete an end-of-study visit. The investigator should record the ESKD event as an adverse event and document the date of dialysis initiation or kidney transplantation.

The reason for discontinuation will be recorded in the eCRF. Reasons for discontinuation may include the following. The standardized disposition term is provided, and details are listed in [brackets]:

- ADVERSE EVENT [Occurrence of an AE or change in medical status that will lead the investigator to be concerned about the patient's welfare];
- DEATH;
- LOST TO FOLLOW-UP [Patient lost to follow-up];
- NON-COMPLIANCE WITH STUDY DRUG [Subject has not agreed with or followed the instructions related to the study medication];
- OTHER [Other specified reason for patient discontinuation];
- PHYSICIAN DECISION [Specified medical reason for patient discontinuation];
- PREGNANCY [Females who become pregnant during the study];
- PROTOCOL DEVIATION [Non-compliance with protocol];

- **PROTOCOL-SPECIFIED WITHDRAWAL CRITERIA MET** [Reached ESKD (initiation of maintenance dialysis for 12 weeks or more or kidney transplant)];
- **STUDY TERMINATED BY SPONSOR** [Sponsor termination of the study];
- **SITE TERMINATED BY SPONSOR** [Premature termination or suspension of an investigational site];
- **WITHDRAWAL BY SUBJECT** [Administrative reasons (eg, inability to continue); Voluntary withdrawal; Withdrawal of consent];

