9.1.9. End Stage Kidney Disease

Patients approaching ESKD should be closely monitored by the investigator to fully characterize their progression. For patients with $eGFR \leq 15.0$ mL/min/1.73 m², initiate more frequent follow-up to closely monitor safety assessments (ie, clinical chemistry (including eGFR), hematology, vital sign assessments (including weight), BNP and N-terminal prohormone B-type natriuretic peptide (NT-proBNP)). Similar frequent follow-up may also be implemented for patients with $eGFR > 15.0$ mL/min/1.73 m² who, in the investigator's opinion based on the anticipated progression of their disease, may be approaching ESKD. Patient follow-up should be completed in-person or through a home health visit where in-person visits are not feasible, at least once every 4 weeks (± 2 weeks), until one of the following occurs:

- Initiation of dialysis;
- Receipt of transplant.

Upon initiation of dialysis, study drug should be temporarily interrupted. Because laboratory and vital sign assessments can be affected by receiving dialysis, those safety assessments should not be performed concurrently while a patient is receiving dialysis. Patients receiving dialysis should continue to be followed for vital status and SAEs by phone or in-person according to the protocol scheduled visits. Dialysis not lasting at least 12 weeks will be considered acute dialysis, and patients should be considered for re-initiation of study drug with medical monitor approval.

After completing acute dialysis, such patients should continue to undergo frequent follow-up (ie, at least once every 4 weeks [± 2 weeks]) while $eGFR \leq 15.0$ mL/min/1.73 m². Study drug may be restarted following acute dialysis, with medical monitor approval. Dialysis lasting at least 12 weeks will be confirmed as maintenance dialysis. Upon confirmation of maintenance dialysis, study drug should be permanently discontinued. Upon receipt of kidney transplant, study drug should be permanently discontinued. See Section 8.5 for description of follow-up options following permanent study drug discontinuation. Initiation of dialysis (acute and/or maintenance) and receipt of kidney transplant due end stage kidney disease should be considered important medical events, and therefore recorded as SAEs.

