#### **8.4.2.2. Frequency of End Stage Kidney Disease, eGFR decline $\geq 30\%$ , or eGFR $< 15$**

The kidney failure composite outcome is defined as reaching one of the following:

- 30% decline from baseline in eGFR; or
- eGFR  $< 15$  mL/min/1.73 m^2; or
- ESKD (initiation of maintenance dialysis or kidney transplant).

A  $\geq 30\%$  decline or eGFR  $< 15$  is considered confirmed when the threshold is achieved at  $\geq 2$  visits. Patients who achieved the threshold at their last visit, and did not have a second confirmatory visit, are considered confirmed. The analysis uses initiation of maintenance dialysis or kidney transplant as reported prior to the end of the follow-up window in the database by the investigator. Any initiation of maintenance dialysis or kidney transplant that occurs after the follow-up window will be listed separately. Patients with a decrease from baseline in eGFR of  $\geq 30\%$  at the last on-treatment visit will be considered to have a  $\geq 30\%$  decrease from baseline eGFR. In the event a patient has both an increase from baseline in eGFR of  $\geq 30\%$  and a decrease from baseline in eGFR of  $\geq 30\%$ , only the decrease from baseline will be considered in composite endpoint analyses.

The proportion of patients with ESKD (dialysis/transplant), eGFR decline  $\geq 30\%$ , or eGFR  $< 15$  will be summarized, and the composite of all these criteria will be evaluated. The frequency analyses will be performed for all visits. No off-treatment eGFR values are included in the analysis.

As a sensitivity analysis, the analyses are repeated for the frequency of patients with ESKD (dialysis/transplant), eGFR decline  $\geq 30\%$ , or eGFR  $< 15$  with all-cause death added to the kidney failure composite.

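### SAP 8.4.1.2 sets all eGFR after any dialysis start to missing, so valid values after recovery from acute dialysis are lost from the by-visit eGFR summaries

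*SAP*

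**What the plan says.** SAP 8.4.1.2 governs the eGFR summaries by visit, the change from baseline and the waterfall plots. It states "Any eGFR values collected after starting dialysis or after receiving a kidney transplant are treated as missing", and then "Missing values are not imputed as specified in Section 6.6.1". It names no type of dialysis and no point at which the rule stops. Elsewhere the SAP is specific: the composite in 8.4.2.2 has the component "ESKD (initiation of maintenance dialysis or kidney transplant", and the SAE definition in 8.1 also refers to maintenance dialysis of 12 weeks or more.

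Protocol 9.1.9 draws the distinction that 8.4.1.2 omits: "Dialysis not lasting at least 12 weeks will be considered acute dialysis". For these patients it says "After completing acute dialysis, such patients should continue to undergo frequent follow-up", at least every 4 weeks while eGFR is 15.0 or lower, and "Study drug may be restarted following acute dialysis, with medical monitor approval". During dialysis, "those safety assessments should not be performed concurrently while a patient is receiving dialysis". Once ESKD is reached (maintenance dialysis of 12 weeks or more, or transplant), protocol 8.5 says "the patient must terminate from the study and should complete an end-of-study visit".

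**The concern.** A rule that discards eGFR during dialysis or after a transplant is sensible, because those values do not describe native kidney function. This rule goes further. A patient who has a short course of dialysis, comes off it and stays under observation has interpretable eGFR again, yet every later value is treated as missing.

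Change from baseline in laboratory results belongs to the primary safety endpoint (protocol 6.2, SAP 3.2.1), and protocol 9.9.13 lists eGFR among the chemistry results. The values are removed because the patient had a severe kidney event, so the missingness is related to outcome. If these patients do worse afterwards than the rest, the visit means will look better than the kidney function of the patients still being followed.

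**Working it through.** The documents state no sample size, event rate or expected eGFR for this study, so there is no figure to reproduce. The check compares the texts and then illustrates the size.

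**1. Which values does the dialysis half of the rule remove?**

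- *During dialysis:* protocol 9.1.9 says the laboratory assessments should not be done, and replaces them with follow-up for vital status and SAEs. There is little to remove.
- *Maintenance dialysis:* the patient leaves the study under protocol 8.5 after an End of Study visit. At most that one sample is removed.
- *After acute dialysis:* the patient stays in the study, may be back on drug, and has eGFR measured. All of these values are removed.

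If the protocol is followed, the dialysis half of the rule therefore acts mainly on valid values after recovery.

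**2. How many values per patient?** SAP 6.5.4 places the windows after Week 24 at 24-week intervals and uses one value per window, the one closest to target. Section 6 of the SAP keeps other unscheduled values out of the summary tables. The loss is 52/24 = 2.2, or about two analysis visits a year.

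**3. Effect on a visit mean.** Let f be the share of patients dropped at a visit. Then

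mean(kept) - mean(all) = f × [mean(kept) - mean(dropped)].

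The sign depends only on whether the dropped patients lie below or above the rest.

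*Change from baseline (assumed values).* Take 100 patients at a visit with a true mean change of +5.0, so the sum is 500. Suppose the affected patients went from a baseline of 19 to 13, a change of -6.

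- 1 dropped: (500 + 6)/99 = 5.11
- 2 dropped: (500 + 12)/98 = 5.22
- 4 dropped: (500 + 24)/96 = 5.46

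*Observed eGFR (assumed values).* Take dropped values of about 15 and other patients at 30 to 60, a gap of 15 to 45 mL/min/1.73 m². The upward shift is f × gap:

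| f | gap 15 | gap 30 | gap 45 |
|---|---|---|---|
| 0.5% | 0.075 | 0.15 | 0.225 |
| 1% | 0.15 | 0.30 | 0.45 |
| 2% | 0.30 | 0.60 | 0.90 |
| 3% | 0.45 | 0.90 | 1.35 |

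Direct check with 200 patients, 2 of them at 15 and 198 at 45: the mean of all is (198 × 45 + 2 × 15)/200 = 44.70, so dropping the two raises it by 0.30, as in the table.

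**4. Does the rule reach the composite in SAP 8.4.2.2?** That section states its own exclusion, of off-treatment eGFR, and neither repeats nor cites the dialysis rule. Acute dialysis is not a component. In the example, 6/19 = 31.6% and 13 is below 15, so both eGFR criteria are met after dialysis. If a programmer carried the 8.4.1.2 rule over, and the patient had restarted drug and first crossed a threshold after dialysis, that patient would not be counted. A patient who had crossed before dialysis could still count, because 8.4.2.2 accepts a threshold met at the last visit without a second confirming visit.

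**The case against.** The strongest reply is that the consequence is limited. The study is descriptive, unpowered and without a comparator, no decision depends on mean eGFR, and the SAP introduction reports that development has been discontinued. Acute dialysis followed by recovery may be rare. All of this bears on importance. It does not make the rule right, because eGFR change by visit is one of the summaries that the study reports.

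Four stronger readings are tempting, and the documents do not support them.

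- *A reader might infer that the worst kidney outcomes vanish from the report.* They do not. Maintenance dialysis, transplant, eGFR < 15 and declines of at least 30% have their own analysis in SAP 8.4.2.2, with death added as a sensitivity analysis. Protocol 9.1.9 has dialysis initiation, acute or maintenance, recorded as an SAE, and SAP 8.1.2 tabulates treatment-emergent SAEs. What remains is that these tables count events and do not show the level of eGFR afterwards.
- *A reader might count every 4-weekly sample as lost, 52/4 = 13 a year.* That is the collection rate while eGFR is 15.0 or lower. Most of those samples would never enter the visit tables.
- *A reader might take the upward direction as proven.* It is plausible, since the protocol expects some of these patients to remain at or below 15.0, but nothing in the documents gives their change relative to the others.
- *A reader might conclude that the composite undercounts.* That follows only if the rule is carried over, and then mainly for patients who restart drug and first cross a threshold later, because off-treatment values are already excluded.

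The objection that the end date of acute dialysis may not be readily available also stands. Protocol 8.5 asks for the initiation date. Protocol 11.6 collects a resolution date for each AE, but nothing says that this is the date of the last dialysis session.

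**Conclusion.** The point holds for the continuous eGFR summaries. Read as written, SAP 8.4.1.2 discards valid eGFR from patients whom the protocol deliberately keeps in the study after acute dialysis. This is a stated rule that conflicts with the protocol's distinction between acute and maintenance dialysis, so adding detail elsewhere would not cure it.

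The loss is about two analysis visits per affected patient per year after Week 24. The number affected is unknown and may be small. Under the assumptions above, the mean change moves from +5.0 to between +5.11 and +5.46, and mean observed eGFR rises by 0.075 to 1.35 mL/min/1.73 m². The upward direction rests on the assumption that these patients' later eGFR, or change in eGFR, is below that of the others. For the composite, the only finding is that the SAP is silent on whether the rule applies.

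**What to change.** Reword SAP 8.4.1.2 so that:

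- eGFR is permanently missing only after kidney transplant, or from the start of dialysis that is confirmed as maintenance (12 weeks or more);
- for an acute episode, eGFR is missing only during dialysis and for a short interval afterwards, with the interval stated in the SAP, and later values are used.

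Add to SAP 8.4.2.2 that the 8.4.1.2 dialysis rule does not remove on-treatment eGFR obtained after acute dialysis, and that the section's existing on-treatment restriction still applies.

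The cost is a few sentences and one programming rule. There are two small downsides. The interval is a convention and should be fixed before database lock. The sponsor must also confirm that the end date of an acute episode can be obtained from the recorded data, and should not assume that the SAE resolution date supplies it. The change concerns data handling only and alters nothing in patient care.
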